6.1. Screening

Screening is the interval between signing the ICF and the date of first dose of study treatment (Day 1). Screening may not exceed 28 days. Assessments that are required to demonstrate eligibility may be performed over the course of 1 or more days during the screening process. Central laboratory results for serum chemistry, hematology, and serology will be used to determine eligibility. Serum pregnancy tests may be performed centrally or at the investigative site laboratory.

Procedures conducted as part of the subject's routine clinical management (eg, imaging study) and obtained before signing of informed consent may be used for screening or baseline purposes, provided that the procedure meets the Protocol-defined criteria and has been performed in the screening interval. All information associated with eligibility requirements must be entered into the appropriate eCRF pages.

Results from the screening visit evaluations will be reviewed by the investigator to confirm subject eligibility before enrollment or the administration of study drug. Tests with results that fail eligibility requirements may be repeated during screening if the investigator believes the results to be in error. For screening assessments that are repeated, the most recent available result before administration of study drug will be used to determine subject eligibility. Additionally, a subject who fails screening may repeat the screening process 1 time if the

investigator believes there has been a change in eligibility status (eg, after recovery from an infection). Such subjects will be assigned a new subject ID number.

6.2. Treatment

The treatment period begins on the date of first dose of study treatment (Day 1). Day 1 must be no more than 28 days after the subject has signed the ICF. Dates for subsequent study visits will be determined based on this date and should occur within the visit windows outlined in the schedule of assessments (see [Table 6](#)) unless delayed for safety reasons. At Day 1, results from screening visit evaluations should be reviewed by the investigator to determine whether the subject continues to meet the eligibility requirements, as specified in the Protocol. Subjects may receive treatment until disease progression, death, unacceptable toxicity, or consent withdrawal.

6.3. End of Treatment

There is no defined date of EOT. When the subject permanently discontinues study treatment, then the EOT visit should be conducted. If the EOT visit coincides with a regular study visit, the EOT evaluations will supersede those of that scheduled visit, and the data should be entered in the EOT visit in the eCRF. The subject should be encouraged to return for the safety follow-up visit.

6.4. Follow-Up

6.4.1. Safety Follow-Up

The safety follow-up period is the interval between the EOT visit and the scheduled follow-up visit, which should occur 30 to 35 days after the EOT visit (or after the last dose of study treatment if the EOT visit was not performed). Adverse events and SAEs must be reported up until at least 30 days after the last dose of study treatment, the date of the follow-up visit, or until toxicities resolve, return to baseline, or are deemed irreversible, whichever is longer. Reasonable efforts should be made to have the subject return for the follow-up visit and report any AEs that may occur during this period.

If a subject is scheduled to begin a new anticancer therapy before the end of the safety follow-up period, then the safety follow-up visit should be performed before new anticancer therapy is started. Once new anticancer therapy has been initiated, the subject will move into the survival follow-up period.

6.4.2. Disease Status Follow-Up

Subjects who discontinue study treatment for a reason other than disease progression will continue to be followed for disease assessments by radiologic imaging per the schedule of

assessments (see [Table 6](#)). Every effort should be made to collect information regarding disease status until 1 of the following occurs:

- The start of new antineoplastic therapy.
- Disease progression.
- Death.
- The end of the study.

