2. STUDY OBJECTIVES AND ENDPOINTS

The primary, secondary, [REDACTED] objectives and endpoints described herein are applicable for both cohorts (Table 1). See Section 9 for details on the analysis of endpoints for each cohort.

Table 1: Study Objectives and Endpoints

Objectives	Endpoints
Primary	
To assess the efficacy of INCB050465 in terms of ORR in subjects with MZL that is relapsed or refractory after at least 1 systemic treatment regimen.	ORR defined as the percentage of subjects with a CR or PR as determined by IRC assessment of response according to CT-based response criteria for lymphomas (Cheson et al 2014).
Secondary	
To assess DOR.	DOR defined as the time from first documented evidence of CR or PR until disease progression or death from any cause among subjects who achieve an objective response, as determined by radiographic disease assessment provided by an IRC.
To assess CRR.	CRR defined as the percentage of subjects with a CR as defined by response criteria for lymphomas (Cheson et al 2014), as determined by an IRC.
To assess PFS.	PFS defined as the time from the date of the first dose of study treatment until the earliest date of disease progression, as determined by radiographic disease assessment provided by an IRC, or death from any cause.
To assess OS.	OS defined as the time from the date of the first dose of study treatment until death from any cause.
To assess the best percentage change in target lesion size.	Best percentage change in target lesion size from baseline, where target lesion size is measured by the sum of the product of diameters of all target lesion sizes.
To characterize the safety and tolerability of INCB050465.	Safety measured by AEs, 12-lead ECGs, chemistry and hematology laboratory values, vital signs, and physical examinations.

Table 1: Study Objectives and Endpoints (Continued)

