5.5.1. Criteria for Study Treatment Discontinuation

Subjects **must** be withdrawn from study treatment for any 1 of following reasons:

- The subject has experienced an unacceptable toxicity defined as follows:
 - Occurrence of an AE that is related to study treatment that, in the judgment of the investigator or the sponsor's medical monitor, compromises the subject's ability to continue study-specific procedures or is considered to not be in the subject's best interest.
 - Persistent AE requiring a delay of therapy for more than 2 weeks (14 days) unless a greater delay has been approved by the sponsor.
- The subject is unable to tolerate study treatment.
- The subject has an objective radiographic tumor response of PD.
- Further participation would be injurious to the subject's health or well-being, in the investigator's medical judgment.
- The subject becomes pregnant.
- Informed consent is withdrawn.
Note: Consent withdrawn means that the subject can no longer be followed. Subjects may choose to discontinue study treatment and remain in the study to be followed for disease progression and survival per the schedule of assessments.
- The study is terminated by the sponsor.
- The study is terminated by the local health authority, IRB, or IEC.

A subject **may** be discontinued from study treatment in the following situations:

- If a subject is noncompliant with study procedures or study treatment administration in the investigator's opinion, then the sponsor should be consulted for instruction on handling the subject.

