6. STUDY ASSESSMENTS

All study assessments will be performed as indicated in the schedule of assessments ([Table 6](#)), and all laboratory assessments will be performed as indicated in [Table 7](#). All assessments mandated throughout the study must be performed on a calendar schedule; delays in treatment administration will not delay performance of assessments. By convention, Week 4, Week 8, Week 12, etc, means the completion of 4, 8, or 12 weeks, respectively. [Table 8](#) presents a summary of clinical laboratory analytes to be assessed. The order of assessments is suggested by the order of mention within the schedule of assessments. See [Section 7](#) for instructions on each assessment.

Table 6: Schedule of Assessments

Procedure	Section	Screening	Treatment			EOT	Follow-Up		
		Days -28 to -1	Day 1 ^a	Every 4 Weeks Through Week 48 (± 3 Days)	Every 12 Weeks From Week 48 (± 1 Week)		Safety	Disease	Survival
							EOT + 30-35 Days		Every 12 Weeks (± 1 Week)
Informed consent	7.1	X							
Contact IWRS	7.2	X	X	X	X	X			
Inclusion and exclusion criteria	3	X	X						
Demography and medical history	7.3	X							
Prior/concomitant medications	7.4	X	X	X	X	X	X		
AE assessment ^d	8.1	X	X	X	X	X	X		
Comprehensive physical exam	7.5.2	X ^e				X			
Disease-specific physical exam	7.5.3		X	X	X		X		
Vital signs	7.5.4	X	X	X	X	X	X		
12-lead ECG	7.5.5	X	X ^f	X ^f	X	X	X		
ECOG performance status	7.5.6	X	X	X	X	X	X		
CT/MRI scan	7.6.1	X		Every 8 weeks through Week 24 (± 1 week), then every 12 weeks through Week 96, and then every 24 weeks thereafter until PD				X ^e	
Bone marrow exam	7.6.2	X ^g			X ^h			X ^h	
Prophylactic treatment for PJP	5.6.1			X ⁱ					
Study treatment dispensing	5.1.1		X	X	X				
Study treatment compliance	5.3		X	X	X	X			
INCB050465 administration	5.2.1		X	X	X				
Disease follow-up	6.4.2							X ^e	
Survival follow-up	6.4.3							X ^j	

^a All procedures are to be performed before administration of study treatment on Day 1.

^d Adverse events will be monitored from the time the subject signs the ICF until at least 30 days after the last dose of study treatment. Serious AEs occurring more than 30 days after the last dose of study treatment should be reported to the sponsor or its designee if the investigator suspects a causal relationship to the study treatment. Once detected, AEs should be followed until resolved or judged to be permanent.

^e Height required at screening only.

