### 7.2. Response Assessment

An objective assessment of disease status is required at baseline (screening) using the CT-based response criteria of the Lugano Classification ([Cheson et al 2014](#)). Disease status will be subsequently assessed by CT/MRI every 8 weeks through Week 24, then every 12 weeks through Week 96, and then every 24 weeks thereafter until disease progression.

Bone marrow examination is required at baseline assessment at screening except for reasons provided in Section 7.6.2 of the Protocol. If disease is present in bone marrow at baseline, a bone marrow examination will be required to confirm CR or may be performed as clinically indicated. If the bone marrow does not have lymphoma involvement at baseline, a repeat marrow examination is not required to confirm indication of CR on imaging. For participants with splenic MZL without measurable disease (ie, only have histologically confirmed bone marrow infiltration), a bone marrow biopsy/examination must be performed when the number of lymphocytes in the blood normalize.

Sites will use the CT-based response criteria of the Lugano Classification ([Cheson et al 2014](#)) to assess response to treatment locally. At each postbaseline disease assessment, response will be collected in the eCRF as CR, PR, SD, PD, or NE.

All imaging will be submitted to an IRC. Imaging data and applicable clinical data will be reviewed and response assessed using the CT-based response criteria of the Lugano Classification ([Cheson et al 2014](#)) by independent reviewers as described in the Independent Review Charter. An overall timepoint response at each postbaseline disease assessment, the best overall response, the date of initial response (if applicable), and the date of disease progression along with reason(s) of disease progression (if applicable) for each participant, considering radiographic data and clinical data, will be provided by the clinical reviewer. Data as determined by the IRC will be used in the analyses of related efficacy endpoints for all participants and participants who have at least 2 prior therapies in the FAS.

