### 7.4.3. Progression-Free Survival

Progression-free survival is defined as the time from the date of the first dose of the study drug to the first documented disease progression as determined by revised response criteria for lymphomas (Cheson et al 2014), or death due to any cause, whichever occurs first. For response assessed by IRC, date of disease progression will be provided by the clinical reviewer. Censoring for PFS will follow the algorithm outlined in Table 2, which is based on FDA Guidance for Industry: Clinical Trial Endpoints for the Approval of Non-Small Cell Lung Cancer Drugs and Biologics (2015) and Guidance for Industry: Clinical Trial Endpoints for the Approval of Cancer Drugs and Biologics (2018).

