**Table 2: Evaluation and Censoring of Progression-Free Survival**

Situation	Outcome	Date of Progression or Censoring
No baseline tumor assessments	Censored	Day 1
No valid postbaseline response assessments	Censored	Day 1
Progression documented between scheduled response assessments	Progressed	Date of first overall response of PD
No progression	Censored	Date of last valid radiologic assessment (not NE and not missing)
Study discontinuation for undocumented progression	Censored	Date of last valid radiologic assessment (not NE and not missing)
Study discontinuation for toxicity or other reason	Censored	Date of last valid radiologic assessment (not NE and not missing)
New anticancer treatment started	Censored	Date of last valid radiologic assessment (not NE and not missing) on/before starting a new anticancer treatment
Death before first progressive response assessment	Progressed	Date of death
Death between adequate response assessments	Progressed	Date of death
Death or progression after 2 or more missed assessments	Censored	Date of last valid radiologic assessment (not NE and not missing) before the missed assessments

NE = not evaluable.

The total number of participants whose disease progressed as determined by IRC or who died and the number of participants censored will be summarized. The Kaplan-Meier estimate of median PFS as determined by IRC and its 95% CIs will be provided, with the CIs calculated using the generalization of Brookmeyer and Crowley's method (1982) with log-log transformation (Klein and Moeschberger 1997). Progression-free survival rates at Month 6, 12, 18, 24, and 36 will also be provided with 95% CIs calculated using Greenwood's formula to estimate the standard error.

A sensitivity analysis of PFS will be performed where response assessments after the time of crossover will be excluded from the determination of PFS for participants who switched to the selected treatment regimen after starting the maintenance dose. Crossover participants who have not progressed at the time of crossover will be censored at the last valid radiologic assessment on/before the time of crossover.

The analyses described above will be summarized for all participants and participants who have at least 2 prior therapies in the FAS.

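### The protocol does not say whose progression call ends imaging, so IRC-assessed PFS and DOR are exposed to informative censoring, probably upward

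*Protocol*

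**What the plan says.** **Endpoint.** Protocol Section 2 (Table 1) runs PFS "until the earliest date of disease progression, as determined by radiographic disease assessment provided by an IRC, or death from any cause". SAP 7.4.3 adds: "For response assessed by IRC, date of disease progression will be provided by the clinical reviewer". SAP 7.4.1 does the same for DOR.

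**Local assessment.** SAP 7.2 states that "Sites will use the CT-based response criteria of the Lugano Classification" "to assess response to treatment locally". Each site records its own call, including PD, in the eCRF. The IRC reads the same imaging separately.

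**Stopping treatment.** Protocol 5.5.1 requires withdrawal from treatment when "The subject has an objective radiographic tumor response of PD". The assessor is not named.

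**Stopping imaging.** Protocol Table 6 schedules scans every 8 weeks through Week 24, "then every 12 weeks through Week 96, and then every 24 weeks thereafter until PD". After treatment ends, 6.4.2 provides that "Subjects who discontinue study treatment for a reason other than disease progression will continue to be followed for disease assessments by radiologic imaging". Section 7.6.1, the synopsis and 4.1 agree. Section 6.4.3 collects tumor assessments during survival follow-up only from participants who stopped for another reason.

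**Censoring.** In SAP Table 2, a participant with no progression is censored at the last valid scan. One who starts a new anticancer therapy is censored at the last valid scan on or before that start. SAP 7.4.1 applies the same rules to DOR.

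**The concern.** Two assessors work in parallel. The endpoint follows the IRC, while the site sees the scan, manages the participant and records why treatment stopped. If the site calls PD and the IRC does not, the text provides no further scans on which the IRC could call it later.

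Kaplan-Meier estimation assumes that participants censored at a given time have the same future risk as those still followed. A participant censored because the site has just seen progression probably does not. The median PFS, the PFS rates at Months 6 to 36 and the median DOR would then look too long. There is no control arm to share such a bias. Durability also matters here: SAP 7.3 times the primary analysis at about 12 months of follow-up from the onset of response.

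**Working it through.** The documents give no figure for PFS, DOR or IRC-site discordance, so there is no planned number to reproduce. The check traces one participant through the text and then illustrates the size under stated assumptions.

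**Tracing one participant**

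1. The site reads a scan as PD, and Protocol 5.5.1 ends treatment.
2. The reason for stopping is progression, so 6.4.2 and 7.6.1 provide no further imaging and 6.4.3 no further tumor data.
3. The IRC reads the same scan as not PD, so there is no IRC progression date.
4. SAP Table 2 censors at the last valid scan, usually that same scan, under the no-progression row or the new-therapy row.
5. A later death is still an event if no new therapy has started and fewer than two assessments have been missed. The SAP does not say whether scans no longer scheduled count as missed.

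**Size by formula**

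Assumptions: a constant progression hazard h, no deaths, and a fraction f of progressions called by the site only and censored just before the IRC would have called them. The observed hazard is (1-f)h, so the median is multiplied by 1/(1-f).

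- f = 10%: 1/0.90 = 1.11
- f = 20%: 1/0.80 = 1.25
- f = 30%: 1/0.70 = 1.43

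Deaths dilute this. If a share d of events are deaths that are always counted, the ratio is 1/(1-f(1-d)). With f = 20% and an assumed d of 20%, it is 1/(1-0.16) = 1.19.

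**Size on the protocol's scan schedule**

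A simulation used 200,000 participants per scenario. Apart from the scan schedule, every input is an assumption: exponential PFS with true median 52, 78 or 104 weeks; f from 10% to 40%; no deaths or new therapy; and, for discordant participants, IRC PD one to three scheduled scans later had imaging continued. IRC PFS with censoring at the site's PD scan was compared with IRC PFS under continued imaging.

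- The 12-month rate rose by 0.7 to 12.4 percentage points.
- The 24-month rate rose by 2.2 to 17.7 points.
- When later IRC progression was unrelated to the site's call, the gap shrank to 0 to 1.7 points at 12 months and 0 to 4.4 at 24 months. What remained came from the coarse scan grid.

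An example with true median 52 weeks and f = 20%. The last row counts every site-called PD as an event. It follows directly from the schedule: the last scans by 52 and 104 weeks are at Weeks 48 and 96, so the rates are 0.5^(48/52) = 0.527 and 0.5^(96/52) = 0.278.

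| Analysis | 12 months | 24 months |
|---|---|---|
| Censored at site PD (current text) | 60.4% | 36.6% |
| Imaging continued, IRC PD one scan later | 54.6% | 28.9% |
| Imaging continued, IRC PD unrelated to site call | 60.0% | 35.6% |
| Site PD counted as event | 52.7% | 27.8% |

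In this example the current rule and the composite bracket both continued-imaging results. The current rule is too high by 5.8 and 7.7 points if IRC PD follows one scan later. The composite is too low by 7.3 and 7.8 points if the site's call carries no information.

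Simulated medians fall only on scan dates and move in steps: 72 against 60 weeks in the one-scan-later case, and 120 against 84 weeks with a true median of 78 weeks. The rates are therefore the steadier measure.

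**The case against.** The strongest reply is that no passage says imaging stops at the investigator's call. Protocol 5.5.1, Table 6, 6.4.2 and 7.6.1 leave the assessor unnamed, and 6.4.3 speaks of confirmed progression without defining it. The IRC's working rules sit in a charter outside these documents, so a confirmation step may exist. This stands. That the site's call governs is an inference from local assessment. It is a natural one, since neither protocol nor SAP mentions a confirmation step.

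Second, investigator-assessed PFS and DOR are planned (Protocol 9.4.1.3; SAP Tables 2.2.2 and 2.2.4). They count the site's PD as an event and so avoid this censoring. SAP Listings 2.6.1 to 2.6.3 and 2.6.7 would let a reader count discordant cases by hand. This stands in part. Those analyses change the assessor for every participant, so they do not isolate the effect of this censoring on the IRC estimate, and no discordance summary is planned. The planned PFS and DOR sensitivity analyses address crossover only.

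Third, PFS and DOR are secondary and descriptive. SAP 7.1 has no hypotheses, and Protocol 4.2 disclaims comparison with historical controls. This limits the consequence but does not remove it.

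A reader might also place these participants under the Table 2 row "Study discontinuation for undocumented progression". That row does not fit. Protocol 5.5 says that stopping treatment is not study completion, and the reasons for leaving the study in 5.7 do not include progression.

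**Conclusion.** The gap is real. The protocol does not name whose progression call ends imaging and does not require the IRC to confirm it, so a site-only PD would usually end in censoring at or near the moment of suspected progression. IRC PFS and DOR are exposed to informative censoring, probably upward, because both assessors apply the same CT-based criteria to the same scans and IRC progression would tend to follow the site's call.

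The size is conditional on an unstated discordance rate. The increases of 11%, 25% and 43% in the median are an upper-end illustration. They assume censoring just before the IRC event and ignore deaths.

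Three stronger readings are tempting but unsupported:

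- **Upward bias is established.** The documents give neither a discordance rate nor the interval to later IRC progression, and the bias nearly vanishes if the two calls are unrelated.
- **Every such participant is censored.** Some later deaths still count as events.
- **The primary result is inflated.** ORR by IRC does not use the progression date, and losing later scans could only remove a late IRC response, which would lower ORR.

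This is a worthwhile, inexpensive improvement to two secondary endpoints. It is not a threat to the primary analysis.

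**What to change.** In SAP 7.4.1 and 7.4.3, add a sensitivity analysis of IRC PFS and DOR in which the event is the earliest of IRC PD, investigator PD that ended scheduled imaging, or death. For DOR, keep the IRC responders and the IRC response date. Beside each result, report how many participants were censored in the main IRC analysis with investigator-only PD.

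The cost is one extra table per endpoint from data already collected. The composite may understate durability where the site's call was wrong, so it should be presented as the lower side of a bracket and not as a replacement for the main analysis.

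Optionally, state in the protocol whose PD call ends imaging and reconcile the synopsis, 4.1, Table 6, 6.4.2, 6.4.3 and 7.6.1. Continuing scheduled scans until IRC PD would reduce the problem further, but it means additional scans for participants, and censoring at the start of a new therapy would still apply. The SAP change does not depend on it.
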